2.1.2 Secondary Objectives

Test the hypothesis that allogeneic MSCs promote endothelial repair through rescue of bone marrow progenitors in type 2 DM patients with symptomatic IHD compared to placebo.

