2.2.2. Secondary Endpoints

Efficacy:

- Cardiac catheterization angiography, CFR and FFR measurement to assess post-coronary angiography coronary artery endothelial function at 6 months post-infusion
- Target lesion lumen loss by QCA at 6 months post-infusion
- Endothelialization and stent site vessel healing parameters by OCT (only applicable if participant undergoes PCI).
- Circulating angiogenic and inflammatory markers at 1-, 3-, and 6-months post-infusion.
- Seattle Angina Questionnaire (SAQ) Angina Frequency and Quality of Life scales at 1-, 3-, and 6-months post-infusion.

Safety:

- Incidence (at one (1) month post-infusion) of any treatment-emergent serious adverse events (TE-SAEs), defined as the composite of: death, non-fatal MI, stroke, hospitalization for heart failure, sustained ventricular arrhythmias (characterized by ventricular arrhythmias lasting longer than 30 sec or with hemodynamic compromise) or atrial fibrillation.

- Incidence of Major Adverse Cardiac Events (MACE), defined as the composite incidence of (1) death, (2) hospitalization for cardiovascular events, or (3) non-fatal MI at 12 months.
- Treatment emergent adverse event (AE) and serious adverse event (SAE) rates through the duration of the study.
- Target Vessel Failure (revascularization, death, or MI attributed to the target vessel) post-PCI (only applicable if participant undergoes PCI).
- Abnormal hematology and clinical chemistry value results.

Exploratory:

- Detailed molecular and functional assessment (genomic, proteomic, proliferation, senescence and differentiation, and angiogenic assays) of bone marrow aspirate at 3 months post-infusion.

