complete the IIEF questionnaire, and only female subjects will be asked to complete the SQOL-F questionnaire.

11. Subjects must be fasting for at least 8 hours prior to blood collection as required by standard of care. If labs were performed as “Standard of Care” within 7 days of signing ICF, those results may be extracted from patient medical records and used for the screening visit in this study. The minimal laboratory requirements include:

Hematology Tests:

Complete Blood Count with Differential (WBC, RBC, hemoglobin, hematocrit, MCV, and platelets; Diff: neutrophils, lymphocytes, monocytes, eosinophils, and basophils).

Chemistry Tests: (fasting required)

Comprehensive Metabolic Panel (glucose, sodium, potassium, chloride, bicarbonate, blood urea nitrogen, creatinine, total protein, albumin, alkaline phosphatase, total bilirubin [fractionate if total >1.5 times normal], alanine transaminase (ALT), aspartate transaminase (AST), and GFR).

Coagulation Tests: Prothrombin time (PT/INR), activated partial thromboplastin time (aPTT).

Urinalysis: Routine Urinalysis with reflex to culture.

Glycosylated Hemoglobin: HbA1c

Biomarkers: SST: (2 Gold or Tiger top serum separator tubes) Transcriptomic/proteome (RNA, mRNA, protein samples, and telomerase, akt); growth factors (sdf-1, notch); functional assays (cell-growth rate, VEGF, and CFU assays), PRA, and more.

Immune monitoring: MNCs: (2 Green top sodium heparin tubes) CD3*CD25* or CD3*CD69* and more.

Gene Expression: peripheral blood will be collected prior to infusion on Day 0, and at the 6 month follow up visit to analyze DNA & RNA (DNA to be collected at one time point only).

EPC-CFU Assay: Blood samples (5 Lavender top tubes) to measure Endothelial Progenitor Cell-Colony Forming Units (EPC-CFU).

Viral Serology: Infectious disease tests – HIV, HIV 2, Hep B (HBsAg), Hep C (Anti-HCV), and CMV.

Serum Pregnancy Test: Serum β HCG test will be completed at screening and within 36 hours prior to infusion in women of childbearing potential only.

If subjects are unable to come to the site for specified visits alternative methods for assessments (e.g., phone contact, virtual visit, alternative location for assessments, including local labs or imaging centers) could be implemented when necessary.

8 Study Phases and Visits

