8.4.5 Laboratory Testing

Gene Expression

A separate blood sample of approximately 17mL for gene expression (DNA) profiling of WBC (at Day 0 OR Month 6 visit) and a separate blood sample of approximately 5.0mL for RNA expression analysis (at Day 0 AND month 6 visits) will be obtained from the study participants, as detailed on Table 1. All samples will be identified so that they can be linked to individual subjects. These samples may be stored indefinitely. Individual results will not be returned to the subject or the study physician. The samples will be linked to subjects, but there will be no recontact. Data presented in publications will not contain individual subjects' clinical characteristics or outcomes; only aggregate data from the entire study will be disclosed. Refer to SOP ISCI QAL-006 (Collection and Transport of Blood Specimens for Clinical Research).

Biomarkers/Immune Monitoring for Graft Rejection

The studies planned in this protocol will utilize allogeneic human bone marrow derived MSCs in subjects with endothelial dysfunction and ischemic heart disease due to the Type 2 DM. The use of an allogeneic graft raises the potential of graft rejection through immune cells resulting in failure of the therapy. MSCs are ideal candidates for allogeneic transplantation because they show minimal MHC class II and ICAM expression and lack B-7 co-stimulatory molecules necessary for T-cell mediated immune responses^{57, 58}. Indeed both types of cells do not stimulate a proliferative response from alloreactive T-cells even when the cells have differentiated into other lineages or are exposed to proinflammatory cytokines. Previous studies have demonstrated that MSCs have significant immunomodulatory effects, inhibiting T-cell proliferation, prolonging skin allograft survival, and decreasing graft-versus-host disease (GVHD). Recently human MSCs were shown to alter the cytokine secretion profile of dendritic cells, T cells, and natural killer cells in vitro, inhibiting secretion of proinflammatory cytokines (e.g. TNF α , IFN- γ) and increasing expression of suppressive cytokines (e.g. IL-10), possibly via a prostaglandin E2 mediated pathway.

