10.2 General Statistical Methods

All statistical tests will be performed at an $\alpha=0.05$ level of significance, using two-sided tests. Because this is a Phase I/II study with only exploratory efficacy outcomes, no adjustments will be made for multiple analyses. Continuous variables will be presented by descriptive statistics. Categorical variables will be presented by counts. Two-sided 95% confidence intervals will be calculated and presented where appropriate.

Analysis of AEs will include tabulation by frequency, severity, organ system affected, and relationship to study exposure. Lung function data will be summarized descriptively.

Subject reported outcome data will be summarized according to the guidelines of each questionnaire.

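### Section 10.2's unadjusted 0.05 rule makes no exception for genomic, proteomic and RNA-expression data; if these are tested feature by feature, individual hits could not support the marrow-progenitor hypothesis

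*Combined protocol and SAP*

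**What the plan says.** The general rule is in section 10.2: "All statistical tests will be performed at an" alpha of 0.05 "level of significance, using two-sided tests". It continues: "Because this is a Phase I/II study with only exploratory efficacy outcomes, no adjustments will be made for multiple analyses". Neither that section nor any other part of the supplied text sets a different standard for high-dimensional data, names a false-discovery procedure, or points to a separate plan for molecular analyses.

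The same protocol schedules three sources of potentially high-dimensional data:

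- Marrow at Month 3. Section 2.2.2 lists under the exploratory endpoints: "Detailed molecular and functional assessment (genomic, proteomic, proliferation, senescence and differentiation, and angiogenic assays) of bone marrow aspirate at 3 months post-infusion". Section 8.3 makes this an optional sub-study with a minimum of 5 participants per arm.
- Blood RNA. Section 8.4.5 provides for "RNA expression analysis (at Day 0 AND month 6 visits"). DNA is taken once only.
- Serum biomarkers. Section 7, note 11 to Table 1, includes "Transcriptomic/proteome (RNA, mRNA, protein samples, and telomerase, akt").

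The marrow work is the listed readout closest to the secondary objective (section 2.1.2), which is worded as a hypothesis to be tested, with the placebo arm as comparator: "Test the hypothesis that allogeneic MSCs promote endothelial repair through rescue of bone marrow progenitors in type 2 DM patients with symptomatic IHD compared to".

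**The concern.** Calling outcomes exploratory is a reasonable ground for leaving a handful of tests unadjusted. A reader can count them and discount accordingly. The reasoning does not carry over to an assay that reads hundreds or thousands of features in one run. There, a 0.05 threshold produces a list of changed genes or proteins even when the cells do nothing, and the list lengthens with the size of the platform.

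What is at stake is narrow. It is whether individual molecular hits can be presented as support for the mechanistic hypothesis in section 2.1.2. The two primary endpoints are not involved.

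**Working it through.** The documents give no feature count, platform, power or expected number of false positives, so there is no figure of the plan's own to reproduce.

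**Inputs from the documents.** Alpha 0.05 two-sided, no adjustment (section 10.2); at least 5 per arm in the marrow sub-study (section 8.3); 15 per arm randomised (section 3.1).

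**Assumed.** The number of features tested in one comparison, m; the share of features that truly change, π; and the power per feature.

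**Step 1: false hits when nothing changes.** The expected number is 0.05 × m, with no independence assumption. The chance of at least one is 1 − 0.95^m, which does assume independent tests.

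| Features m (assumed) | Expected false hits | Chance of at least one |
|---|---|---|
| 10 | 0.5 | 40% |
| 100 | 5 | 99.4% |
| 200 | 10 | about 100% |
| 1,000 | 50 | about 100% |
| 5,000 | 250 | about 100% |
| 20,000 | 1,000 | about 100% |

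**Step 2: share of hits that are false when some features do change.** The share is 0.05(1 − π) / [0.05(1 − π) + power × π]. It does not depend on m.

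- π = 1%, power 30%: 0.0495 / (0.0495 + 0.003) = 94%. Power 80%: 0.0495 / (0.0495 + 0.008) = 86%.
- π = 5%, power 30%: 0.0475 / (0.0475 + 0.015) = 76%. Power 80%: 0.0475 / (0.0475 + 0.04) = 54%.
- π = 10%, power 79% (a 2-SD difference at 5 per arm): 0.045 / (0.045 + 0.079) = 36%.

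**Step 3: what adjustment costs at 5 per arm.** For a 2-SD difference, an ordinary two-sample t-test has power of 79% at 0.05, 2.6% at 0.05/500 and 0.1% at 0.05/20,000. The last two are Bonferroni levels. The Benjamini-Hochberg procedure is less strict than that, but comes close to it when few features change.

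**Step 4: which test the fix can use.** An exact two-sided rank test at 5 v 5 cannot give a p-value below 2/252 = 0.0079. To pass Benjamini-Hochberg, the share of features reaching that minimum would have to be about 0.0079/0.05 = 16% at a 5% false discovery rate, or 0.0079/0.10 = 7.9% at 10%. At 6 v 6 the minimum falls to 2/924 = 0.0022. This bears on the choice of method in the fix. It is not a fault in the plan, which names no rank test.

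**The case against.** The strongest reply is that the plan never says these data will be tested feature by feature. Section 10.2 also provides for descriptive summaries, and its reason for not adjusting refers to efficacy outcomes, whereas section 2.2.2 lists the marrow work separately as exploratory. Section 8.4.5 treats the stored samples largely as a repository for later research. The analytes named individually (telomerase, akt, sdf-1, notch, VEGF and the T-cell markers) would suit a small targeted panel. All of this stands, and it makes the point conditional. It does not remove the point, because the only rule supplied covers all tests and nothing exempts these.

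Two stronger readings are tempting and should be resisted.

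- A reader might infer that the plan will produce up to a thousand false hits. The documents do not support this, since they state no feature count. With 10 to 100 markers the expected number is 0.5 to 5.
- A reader might infer that the mechanistic readout would be uninterpretable or would carry no evidence. That is also too strong. Under the assumptions in step 2, between 6% and 64% of hits would be real, so an unadjusted list can rank candidates, which is a fair use of an exploratory endpoint. Moreover, the proliferation, senescence, differentiation and angiogenic assays are not shown to be high-dimensional, and they bear on the progenitor hypothesis at least as directly as a gene list. So does EPC-CFU.

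The sample size deserves the same care: 5 per arm is a minimum, and section 8.3 expects more than 10 sub-study participants in total.

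**Conclusion.** The concern holds in conditional form. As worded, section 10.2 governs any test on the genomic, proteomic and RNA-expression data. If those data are tested feature by feature, about 5% of unaffected features will be called significant in each comparison, from 0.5 at 10 features to 1,000 at 20,000. At that standard an individual hit could not be offered as evidence for the secondary hypothesis, although the list could guide further work.

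The counts rest on assumed feature numbers, and the false shares on assumed rates of true change and power. The existence of the gap rests on neither. It is worth correcting, but it is confined to the molecular platforms and leaves the primary endpoints, the functional assays and EPC-CFU as they are.

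**What to change.** In section 10.2, limit the no-adjustment sentence to the low-dimensional endpoints. For each high-dimensional platform, state the number of features and then take one of two routes.

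1. **Testing.** Name one MSC-versus-placebo contrast: the Month 3 level for marrow, and the Day 0 to Month 6 change for blood RNA. If the serum panel proves to be high-dimensional, it also needs a single contrast chosen in advance. Control the Benjamini-Hochberg false discovery rate within the platform at a level fixed before unblinding, for example 5% or 10%, and report adjusted values. Use a test that can reach small p-values at about 5 per arm, such as a moderated t-statistic.
2. **Description.** Report the platform descriptively, with no significance claims.

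A small targeted panel can stay under the existing rule if its size is stated.

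The change needs no new visits, samples or participants. It is a short addition to the plan, but the platforms and feature sets must be settled first. The real cost is in the yield: with as few as 5 per arm, few or no individual features will be declared changed.

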3. STUDY DESIGN

3.1 Description of the Study

Thirty (30) patients meeting the inclusion/exclusion criteria will be randomized to receive either allogeneic MSCs or placebo in a 1:1 blinded fashion:

- Group A (15 patients) – Allogeneic MSCs: 100 million cells delivered intravenously.
- Group B (15 patients) – Placebo: Cell-free PlasmaLyte-A medium supplemented with 1% HSA

A separate sub-study will be conducted in which a bone marrow biopsy will be obtained at 3-month time point from patients participating in each group.

4. SUBJECT SELECTION

4.1. Inclusion Criteria

In order to participate in this study, a subject MUST:

1. Be ≥ 18 years of age (males and females).
2. Provide written informed consent.
3. Have a diagnosis of symptomatic ischemic heart disease (IHD) and an indication for standard-of-care coronary angiography.
4. Have type 2 diabetes mellitus documented by hemoglobin A1C $> 7\%$, or on medical therapy for type 2 diabetes mellitus.

4.2. Exclusion Criteria

In order to participate in this study, a subject MUST NOT:

1. Be younger than 18 years of age.
2. Have a baseline glomerular filtration rate (GFR) < 30 ml/min 1.73m^2 estimated using the MDRD formula.
3. Indication for surgical revascularization or valve therapy.
4. Have known hypersensitivity or contraindication to aspirin; both heparin and bivalirudin; all available P2Y₁₂ inhibitors (clopidogrel, prasugrel, and ticagrelor); or

- any zotarolimus, cobalt, chromium, nickel, tungsten, acrylic, or fluoropolymers; or hypersensitivity to contrast media that cannot be adequately premedicated.
5. Have a hematologic abnormality as evidenced by hematocrit < 25%, white blood cell < 2,500/uL or platelet values < 100,000/uL without another explanation (per investigator discretion).
 6. Have liver dysfunction, as evidenced by enzymes (AST and ALT) greater than three times the upper limit of normal.
 7. Have a bleeding diathesis or coagulopathy (INR > 1.3), cannot be withdrawn from anticoagulation therapy, or will refuse blood transfusions.
 8. Be an organ transplant recipient or have a history of organ or cell transplant rejection.
 9. Have a clinical history of malignancy within the past 2 years (i.e., subjects with prior malignancy must be disease free for 2 years), except curatively treated basal cell or squamous cell carcinoma, or cervical carcinoma.
 10. Have a condition that limits lifespan to < 1 year.
 11. Have a history of drug or alcohol abuse within the past 24 months.
 12. Be serum positive for HIV, hepatitis B sAg, or viremic hepatitis C.
 13. Be currently participating (or participated within the previous 30 days) in an investigational therapeutic or device trial.
 14. Be pregnant, nursing, or of childbearing potential and not on contraceptive medications. (May participate if on 2 forms of contraceptives).
 15. Any other condition that in the judgment of the Investigator would be a contraindication to enrollment or follow-up.

4.3. Concomitant Treatments, Procedures, and Nondrug Therapies

All concomitant medications (prescription or over-the counter) as well as procedures or nondrug therapies (e.g. continuous positive airway pressure, cardiac rehabilitation) will be recorded at the initial screening visit and updated at each subsequent visit. Except for other experimental treatments or medications with putative disease modifying effects in endothelial dysfunction, subjects will continue all prior concomitant medications for comorbid diseases to ensure optimal general medical care.

4.4. Withdrawal Criteria

Subjects will be informed that they have the right to withdraw from the study at any time and for any reason without prejudice to future or continued medical care. Subjects must be withdrawn for the following reasons:

- Subject's request.
- Subject is unable or unwilling to comply with the protocol.
- Medical reasons, at the discretion of the investigator.

Reason for withdrawal will be recorded in the subject's case report form. In order to adequately monitor for safety and potential efficacy outcomes, subjects who are withdrawn for any reason after receiving the first infusion should be encouraged to return for all assessments through the end of the study period. All efforts should be made to continue to record safety data and lung function parameters for all withdrawn subjects.

Subjects who withdraw for reasons unrelated to the study or study drug (e.g. withdrawal of consent or loss to follow-up) may be replaced if deemed necessary to meet study objectives. Replacement subjects will be assigned unique identification numbers.

5. DONORS

5.1 Normal Donor Eligibility and Screening

Healthy volunteers (male or female) between the ages of ≥ 18 to ≤ 45 (inclusive) will be screened as potential bone marrow donors. Screening of allogeneic donors will follow standard transplant practices and all allogeneic donors will meet allogeneic donor eligibility criteria as outlined in 21 CFR Part 1271 and as specified in the POSEIDON-DCM trial (IND#: 14419; NCT01087996), ACESO trial (IND#: 17054; NCT02886884), and FDA Drug Master File (DMF)# 17882. Donors will be consented and evaluated as per the current IRB approved DONOR protocol (eProst#: 20171033). All screening tests will be performed in accordance with the DONOR protocol (eProst#: 20171033).

6. TREATMENT OF SUBJECTS

6.1 Study Investigational Product

The investigational product (IP) consists of MSCs obtained from a healthy donor of bone marrow or from a commercial clinical grade bone marrow source. Screening of allogeneic donors will follow standard transplant practices and all allogeneic donors will meet allogeneic donor eligibility criteria as outlined in 21 CFR Part 1271 and as specified in the POSEIDON-DCM trial (IND #: 14419; NCT01087996), ACESO trial (IND#: 17054; NCT02886884), and FDA Drug Master File (DMF)#: 17882. BM will be obtained from normal volunteers and aspirated from the posterior iliac crest. The BM will be aspirated into heparinized syringes. The MNC fraction will be isolated using a density gradient with Lymphocyte Separation Media (specific gravity 1.077). The low-density cells will be collected and washed with Plasma-LyteA containing 1% HSA. The MNCs will be prepared with or without antibiotics. Subjects with a penicillin allergy will not receive antibiotic treated cells. The washed cells will be samples and viable cell numbers determined. The BM MNC will be seeded into 175 cm² tissue culture flasks in alpha MEM containing 20% FBS. After 14 days of culture, passage zero (P0) cells will be harvested by trypsin treatment and expanded into 60 flasks (P1 cells). After 7 to 10 days P1 cells are harvested by trypsin treatment (P1 cells). Cells from P1 will be cultured for 7 to 10 days and harvested by trypsin treatment and expanded into 180 flasks (P2 cells) with the option of expanding them once again, to P3. After 7-10 days P3 cells would be harvested by trypsin treatment and cryopreserved.

Before dispensing the investigational product, Cell Therapy Lab staff will confirm the CMV status of eligible recipients. This information will be used to select the Allo-hMSC product. CMV status of the recipient and donor of the Allo-hMSC product will be matched. CMV positive Allo-hMSC product will only be infused to a CMV positive recipient. All CMV negative recipients will receive CMV negative Allo-hMSC product⁹¹.

6.2 Dosing

The allogeneic MSCs are manufactured by the University of Miami Interdisciplinary Stem Cell Institute, as specified in the DONOR protocol (eProst#: 20171033) and FDA DMF#: 17882. The 100 million dose of MSCs has been validated in multiple published clinical trials by our group[9-13, 31, 32, 46, 47] and other groups as well as in the ongoing ACESO pilot study (IND#: 17054; NCT02886884; data shown above).

6.3 Dosage Rationale

A safety profile for IV infusion of MSCs was based on outcomes from previous completed toxicology results[10, 49]. The results from these previous studies demonstrate that the product can be administered intravenously without toxic events at up to 65×10^6 MSC/kg dose delivered in one bolus infusion or at 100×10^6 MSC/kg cumulative dose delivered by 5 infusions (20×10^6 MSC/kg per infusion).

The evidence supports the conclusion that it is feasible to dose subjects in this study based on a standard dose of MSCs rather than per kilogram of body weight. The total cell number corresponds to a range of $1.3 - 4.4 \times 10^6$ MSCs per kg per infusion for subjects with 45kg to 150kg body weight.

In addition, the data from the administration of allogeneic MSCs in the DCM (IND #: 14419; NCT01087996) trial supports the clinical safety of the proposed MSC doses to be administered. Therefore, results from previous trials support the rationale on the safety and potential efficacy of the selected maximum dose of 100×10^6 allogeneic MSCs.

A previous pilot study was conducted to compare the effects of two different doses of MSC given via IV infusion in type 2 diabetic subjects (ACESO). The results of this study showed that both the 20 and 100 million cell doses are safe but the 100 million dose was the optimal dose and was selected to be used for this study (results showed above).

